Statistical Methods	
The primary efficacy analysis, the rate of complete healing, will be based on the logistic regression model for the binary response that will be used to test for the differences in the treatment efficacy between ON101 cream and Aquacel[®] Hydrofiber[®] dressing. The logistic model will include treatment group and the following prognostic factors: baseline wound size and baseline Wagner grade. The comparison between the two treatment groups will be presented in term of the odd ratios, with p-values and associated 95% confidence intervals of the odds ratio. Two interim analyses will be conducted at about 118 and 212 subjects complete the comparison period or early withdraw from study intervention on a sequential basis. This will be about 50% and 90% of the total number of subjects that will be randomized. The final analysis will be conducted at the end of study. The futility/superiority of ON101 cream will be assessed using the Lan-DeMets approach which the boundaries are determined by the type of O'Brien-Fleming spending function.
 
The wound size will be compared between groups by means of analysis of co-variance (ANCOVA). The method of Kaplan and Meier will be used to summarize the time to event data. The difference in time to complete ulcer healing between the treatment groups will be analyzed by the log-rank test.
 
For the safety parameters, numerical comparisons between treatment groups in adverse events (AEs), vital signs and safety laboratory results based on change from baseline will be provided.

V. FLOW CHART AND SCHEDULE OF ASSESSMENTS

Flow Chart

Obtaining informed consent		Screening Period		Confirmation of entry criteria		Randomization		Administration period (up to 16 weeks)	Follow-Up (up to 28 weeks)
	→	Standard Care	→		→		ON101 cream (BID)	Aquacel [®] Hydrofiber [®] dressing (for non-healing wound)	
			→		Aquacel [®] Hydrofiber [®] dressing				

Schedule of Assessments

Assessments	Screening	Baseline	Comparative Period (up to 16 weeks)								Follow-Up [@]			
			3	4	5	6	7	8	9	10 ^{&}	11	12	13	14
Visit Number	1	2 [#]	3	4	5	6	7	8	9	10 ^{&}	11	12	13	14
Visit Weeks	-1		2	4	6	8	10	12	14	16	18	20	24	28
Visit Days	-7	1*	15	29	43	57	71	85	99	113	127	141	169	197
Allowed visit window(days)	-3		±4	±4	±4	±4	±4	±4	±4	±4	±4	±7	±7	±7
Informed consent	X													
Randomization		X												
Apply test medication or comparative intervention		X	X	X	X	X	X	X	X	X [@]	X [@]	X [@]	X [@]	X [@]

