7.4 Analysis of Efficacy

7.4.1 Analysis of Primary Variable

The primary efficacy variable is the proportion of subjects whose target ulcer is complete healing. The definition of complete healing for the target ulcer is complete epithelialization which is maintained with no drainage for at least 2 weeks and is confirmed by a blinded independent evaluator.

This will be a multi-center study. It is anticipated that the number of participating centers can be large and the number of subjects enrolled at each center could be small. As a result, the data from all centers will be pooled for statistical analyses.

The hypothesis for the comparison is given as follows:

H_0 : The healing rates on ON101 cream and Aquacel® Hydrofiber® dressing are the same

H_1 : The healing rates on ON101 cream and Aquacel® Hydrofiber® dressing are not the same

The number of percentage of subjects achieving the efficacy endpoints will be summarized by visit and ON101 cream group will be compared to the Aquacel[®] Hydrofiber[®] dressing group with Chi-square test. The logistic regression model with treatment/intervention as fixed factor, and baseline wound size and Wagner grade as covariates will be applied to the primary analysis of primary endpoint. The results of the logistic regression model will be presented in terms of the odd ratio (ON101 cream versus Aquacel[®] Hydrofiber[®] dressing), with p-values and associated 95% confidence intervals of the odds ratio.

The test intervention (ON101 cream) will be concluded to be superior to the control (Aquacel[®] Hydrofiber[®] dressing) in average if the null hypothesis (H_0) is rejected and the odds ratio higher than 1. To reflect the interim analysis, final analyses will be based on a Type I error rate (two-sided) of 0.039611.

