7.4.2 Analysis of Secondary Variables

The secondary efficacy variables will be analyzed using FAS population.

- Time to complete ulcer healing:

Time to complete ulcer healing will be calculated for all subjects from the day of the first study medication applied until the day that original healing of target ulcer is first observed. Subjects who could not achieve complete ulcer healing at the last evaluation time point will be censored (non-healing) at the date of last evaluation. The median time to complete ulcer healing will be estimated by Kaplan-Meier method and two-sided 95% confidence interval will be reported. The log-rank test will be performed for comparing time to complete ulcer healing among two groups.

- Percentage change in ulcer surface area from baseline:

Summary statistics of the measured wound size and the percentage change from baseline will be obtained for each group by observation time point and their changes over time will also be graphically presented.

For the analysis on the ulcer surface area, the percentage change from baseline at each visit will be calculated using the actual wound size. The wound size percentage change will be compared between groups by means of analysis of co-variance (ANCOVA) adjusted with baseline measurement of sizes and baseline Wagner grade.

- Percentage of subjects with a 50% reduction of ulcer surface area:

The proportion of subjects who achieve 50% reduction of wound size from baseline to interim visit will be calculated for two groups and analyzed by a logistic regression model with treatment as factor, and baseline wound size and Wagner grade as covariates.

- Incidence of infection of the target ulcer:

The incidence of infection of the target ulcer will be summarized and tabulated by two treatment groups at the final ulcer assessment. The incidence of infection of target ulcer between two groups will be compared using Fisher's exact test.

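### Time to healing is tested only by an unadjusted log-rank test, although the plan calls baseline ulcer area and Wagner grade prognostic and adjusts every regression-based efficacy analysis for both; adjusting here would be a cheap gain in efficiency and consistency

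*Combined protocol and SAP*

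**What the plan says.** Section 7.4.2 (time to complete ulcer healing) plans Kaplan-Meier medians with confidence intervals and then: "The log-rank test will be performed for comparing time to complete ulcer healing among two groups". The Synopsis (Statistical Methods) agrees: "The difference in time to complete ulcer healing between the treatment groups will be analyzed by the log-rank test". Neither place mentions strata, covariates, a Cox model or a between-group effect estimate.

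For the primary endpoint the Synopsis states: "The logistic model will include treatment group and the following prognostic factors: baseline wound size and baseline Wagner grade". Three analyses adjust for both factors:

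- primary endpoint, Section 7.4.1: "The logistic regression model with treatment/intervention as fixed factor, and baseline wound size and Wagner grade as covariates"
- percentage change in area, Section 7.4.2: "analysis of co-variance (ANCOVA) adjusted with baseline measurement of sizes and baseline Wagner grade"
- 50% area reduction, Section 7.4.2: "analyzed by a logistic regression model with treatment as factor, and baseline wound size and Wagner grade as covariates"

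Other efficacy comparisons are unadjusted. For infection, Section 7.4.2 says: "The incidence of infection of target ulcer between two groups will be compared using Fisher's exact test". Recurrence (Section 7.4.3) is also compared by Fisher's exact test, and Section 7.4.1 adds a by-visit chi-square test.

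**The concern.** Factors regarded as prognostic for whether an ulcer heals within 16 weeks are hard to treat as irrelevant to how soon it heals. Eligibility is broad (Section 3.2: grade 1 or 2, 1 to 25 cm²), so patients may differ widely in their chance of healing. When strong prognostic factors are left out, a log-rank test loses some power to detect a real difference in healing speed.

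Section 4.5 describes randomization in blocks by site and states no stratification by area or grade. A chance imbalance would therefore be allowed for in the primary result but not in the time-to-healing result, and the two could point different ways for that reason alone. Section 7.4.2 gives no reason for the different treatment.

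**Working it through.** **1. The plan's own sample size.** Inputs from Section 7.1: 50% versus 30%, two-sided 5%, 80% power, 1:1 allocation, looks at about 50%, 90% and 100% of information, 10% non-evaluable.

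- Per arm: [1.96·√(2·0.4·0.6) + 0.8416·√(0.25+0.21)]² / 0.2² = 93.
- With continuity correction: 103 per arm, 206 in total.
- Times 1.0253 for O'Brien-Fleming-type spending: 211.2, so 212. Then 212/0.9 = 235.6, so 236.

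Both stated figures reproduce. The point does not rest on a sample-size error.

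**2. Power of the planned log-rank test.** The plan states none for this endpoint.

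- Hazard ratio implied by the planning rates: ln(0.5)/ln(0.7) = 1.94.
- Schoenfeld events for 80% power: 4·(1.96+0.8416)²/(ln 1.94)² = 72.
- Expected healings: 0.40·212 = 85 and 0.40·236 = 94.
- Power = Φ(√events·ln(1.94)/2 − 1.96): 86% at N=212 and 90% at N=236.
- At the 0.039611 that Section 7.4.1 sets for the final analysis (z = 2.058): about 84% and 88%.

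**3. What adjustment adds.** The prognostic strengths are assumptions. The same hazard ratio was applied per e-fold (2.72 times) of area and for grade 2 versus 1. To show the scale: ln 25 = 3.22, so from 1 to 25 cm² the hazard falls 2.0-fold at 0.8, 4.0-fold at 0.65 and 9.3-fold at 0.5.

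Other assumptions:
- exponential healing times seen at two-weekly visits
- log area about normal (median 5 cm², SD 0.8, limited to 1–25 cm²)
- half the subjects at grade 2
- 10% random dropout
- overall healing fixed at 30% and 50%
- two-sided 5%, 3,000 trials per row (simulation error of each power about 0.6 points)

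| N | Assumed HR | Log-rank | Stratified log-rank | Cox, adjusted | Cox minus log-rank |
|---|---|---|---|---|---|
| 212 | 1.0 | 85.0% | 84.1% | 84.2% | −0.8 |
| 212 | 0.8 | 82.9% | 82.6% | 82.8% | −0.1 |
| 212 | 0.65 | 84.9% | 86.4% | 87.5% | +2.6 |
| 212 | 0.5 | 86.2% | 89.4% | 91.1% | +4.9 |
| 236 | 1.0 | 88.1% | 87.5% | 87.4% | −0.7 |
| 236 | 0.8 | 87.4% | 87.1% | 87.5% | +0.1 |
| 236 | 0.65 | 88.2% | 89.2% | 90.0% | +1.8 |
| 236 | 0.5 | 89.0% | 92.0% | 93.6% | +4.6 |

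The three tests share the same simulated data, so comparisons within a row are firmer than comparisons between rows. The stratified test (by grade and median area) gains −0.9 to +3.2 points. A repeat run at N=212 (1,500 trials per setting) gave plain versus stratified 83.3 vs 82.4%, 84.9 vs 84.6%, 85.3 vs 86.3% and 84.6 vs 88.6%, in the same order of assumed hazard ratios.

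**4. Type I error.** With covariate hazard ratios of 0.5 and no treatment effect (4,000 trials, N=212): 4.6%, 4.6% and 4.4%. All three tests are valid.

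**5. Chance imbalance, as illustration.** With 118 per arm and an assumed 50% at grade 2, the standard error of the between-arm difference is √(2·0.25/118) = 6.5 points. A gap of 10 points or more (z = 1.54) arises about 12% of the time.

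**The case against.** The other side is strong on several counts. The unadjusted test is valid, matches the planned Kaplan-Meier display, and serves a secondary endpoint for which no power is claimed. The plan also has a recognizable pattern of covariates in regression models and none in non-parametric tests. All of this stands, and it makes the point one of efficiency rather than correctness.

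A reader might infer more than the documents support:

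- *That time to healing alone ignores the two factors.* It does not. The Fisher tests for infection and recurrence and the by-visit chi-square test are also unadjusted.
- *That adjustment costs nothing.* With no prognostic effect it loses up to about 1 point, and at 0.8 it gains essentially nothing.
- *That the trial wastes the equivalent of 10% to 20% of its subjects, or 10 points of power.* Figures of that size need large assumed effects. For example, log-hazard effects of 0.6 to 0.8 per log unit of area mean a 6.9- to 13-fold range in hazard over 1–25 cm², with a grade effect on top. The documents give nothing to support such values.

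Sections 7.2 and 7.6.2 refer to a separate statistical analysis plan, which might contain an adjusted analysis. The text available here does not show one. If it exists, Section 7.4.2 and the Synopsis still need to agree with it.

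The timing objection also stands: Section 7.6.2 reports that the first interim analysis has been done and missed its boundary, and under Section 4.4 investigators know the assignment. A change now is therefore more than an edit of one sentence.

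**Conclusion.** The point holds as a worthwhile improvement, not as an error. The plan itself calls area and grade prognostic, collects both before treatment and adjusts every regression-based efficacy analysis for them. It then leaves them out of the test for the secondary endpoint closest to the primary.

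The planned test already has about 83% to 90% power under the planning rates. Adjustment by Cox model or stratification changes this by about −1 to 0 points for assumed hazard ratios of 1.0 to 0.8, about +1 to +3 at 0.65, and about +3 to +5 at 0.5. The gain is therefore real only if the factors are at least moderately prognostic. The plan's label supports that direction but not any particular size. Neither invalidity nor low power of the planned test can be claimed.

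**What to change.** In Section 7.4.2 and the Synopsis, make the between-group test for time to healing the treatment term of a Cox model with baseline Wagner grade and log baseline ulcer area. These are the primary model's factors, and no arbitrary area cut is needed. Specify the handling of ties (for example Efron), because healing is seen at two-weekly visits. Report the adjusted hazard ratio with its 95% confidence interval, which also supplies the effect estimate that Section 7.4.2 lacks. Keep the Kaplan-Meier estimates and the unadjusted log-rank test as supportive.

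Make the change by a documented amendment, giving the reason, before anyone deciding it sees unblinded comparative results.

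Cost: no new data and a short text change, but also an amendment after an interim analysis. Power falls by up to about 1 point if neither factor is prognostic. The result rests on proportional hazards and describes a conditional effect, that is, at given area and grade.

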2.2 Study Design and Dose Rationale

2.2.1 Study Design and Rationale

This trial is designed as a randomized, evaluator blinded, active-controlled, multi-center study comparing the efficacy and safety of ON101 cream and Aquacel® Hydrofiber® dressing in the treatment of diabetic foot ulcers. An independent evaluators who blinded to subjects' treatment will evaluate whether the wound has healed, defined as epithelialization wound. Subject with Type 1 or 2 diabetes mellitus (DM) and with Wagner Grade 1 or 2 diabetic foot ulcer (DFU) of neuropathic or neuro-ischemic etiology will be included in this study. If there is more than one ulcer on the foot, the most severity then largest ulcer that confirmed to the inclusion/exclusion criteria will be selected for study evaluation. Eligible subjects will be randomized to receive either ON101 cream or Aquacel® Hydrofiber® dressing in a 1:1 allocation. The study treatment will be applied to the selected ulcer for a maximum period of 16 weeks, until the wound/ulcer closure (wound size of 0) for two consecutive visits at least 2 weeks apart, or until the subject exited the study as treatment failure. After that, all subjects regardless of wound healing at the end of comparison period will be followed for 12 weeks to investigate durability. During the follow-up period, Aquacel® Hydrofiber® will be applied for subjects who have unhealed or with recurrence wound. Each target ulcer with wound photographs for blind assessment will be monitored at each scheduled visit.

Two interim analyses will be conducted at around 50% and 90% of study information; the final analysis will be conducted at the end of the study. The futility/superiority of ON101 cream will be assessed using the Lan-DeMets method with O'Brien-Fleming spending boundaries.

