3.4 Discontinuation Criteria for Individual Subjects

A discontinuation is a subject who is randomized into the study and for whom study treatment is terminated prematurely for any reason.

The subject is free to withdraw from the study intervention and/or study for any reason and at any time without giving reason for doing so and without penalty or prejudice. The investigator is also free to terminate a subject's involvement in the study at any time if the subject's clinical condition warrants it.

Discontinuation Criteria for Individual Subjects:

1. Violation and/or significant deviation of study protocol
2. Lack of efficacy satisfactory (defined as a worsening of Wagner grade to level of 3)
3. Safety concerns
4. Lost to follow-up
5. Withdrawal consent;
6. In the Investigator's opinion, it is in the patient's best interest;
7. Termination of study by the sponsor.

In all cases, the reason for and date of withdrawal must be recorded in the case report form (CRF) and in the subject's medical records. The subject must be followed up to establish whether the

reason was an adverse event, and, if so, this must be reported in accordance with the adverse events reporting procedures.

If a subject withdraws from the study or the study intervention is discontinued prematurely, all procedures as scheduled at the end of the trial should be included on the case report form.

There will be no replacement of withdrawn subjects, regardless of the reason for withdrawal. All subjects who experience adverse event which is ongoing either at the time of withdrawal or at the post study visit, must be followed-up at appropriate time intervals until the adverse event is resolved or judged to be no longer clinically significant, or until they become chronic to the extent that they can be fully characterized.

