5.3.3 Diagnosis of the Target Disease, Severity, and Duration of Disease

Please refer to “Diabetic Foot Disorders: A Clinical Practice Guideline (2006 revision)” as Appendix 1.

The following target ulcer characteristics should be collected before randomization:

- Duration of diabetic foot ulcer
- Ulcer severity (Wagner grade)
- Ulcer etiology (Neuropathic, Neuro-ischemic)
- Ulcer location (Plantar, Non-plantar)

Although no single system has been universally adopted, the classification system most often used was described and popularized by Wagner. In the Wagner system, foot lesions are divided into six grades based on the depth of the wound and extent of tissue necrosis.

Grade 0: No open lesion, may have deformity or cellulitis

Grade 1: Superficial ulcer

Grade 2: Deep ulcer to tendon or joint capsule

Grade 3: Deep ulcer with abscess, osteomyelitis, or joint sepsis

Grade 4: Local gangrene – forefoot or heel

Grade 5: Gangrene of entire foot

The major aetiologies of DFUs are neuropathy (nerve damage), neuroischaemia and peripheral vascular (arterial) disease. Some 40–70% of DFUs are caused by neuropathy, 15–24% by peripheral vascular disease and 15–45% by neuroischaemia.

The neuropathic foot is typically warm to touch with good perfusion and palpable pulses. The skin may be anhydrotic (dry) and prone to fissuring and callosities. Ulcers often occur on the plantar surface, principally under the metatarsal heads in the forefoot. They are round and surrounded by callus.

The neuroischaemic foot is typically cool to touch and has poor perfusion, characterized by diminished or absent foot pulses. The skin is usually atrophic, anhydrotic and shiny. Hair growth is often minimal and atrophy of the subcutaneous tissues is apparent. Ischaemic ulcers often occur on the digits and heels, and are usually dry with vertical walls. Necrotic tissue may be present.

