5.4 Efficacy Assessment

The efficacy assessment is based on the subject's wound size. It will be conducted at clinic by digital planimetry method at baseline and every 2 weeks after study intervention until wound closure (wound size of 0) has confirmed 2 weeks apart, or until the study subject exited the study as lack of efficacy satisfactory.

The digital planimetry method involves applying a two-layer transparent acetate over the wound and tracing the perimeter with a permanent pen. The contact layer is then discarded into clinical waste and the top layer stored within the subject notes. The top layer is placed on a digital tablet, and the border is re-traced using a stylus. The underlying sensor then calculates the wound area.

For the purpose of this study a complete healing will be defined as complete epithelialization which is maintained with no drainage for at least 2 weeks and is confirmed by a blinded independent evaluator. At each clinic visit after study intervention, digital photographs should be taken of study wound after the area had been carefully shaved to visualize the wound margin and for better visualization of epithelialization and granulation tissue area.

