7.7 Handling of Missing Data

All available data will be displayed and utilized in data analysis. Under the ITT principle, the subject will be considered as “non-healing” if no available data for post-baseline wound/ulcer healing assessment. Otherwise, the method of last observation carry forward (LOCF) will be used to account for incomplete observation.

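### A subject who exits as a treatment failure (Wagner grade 3) can still be scored as a 50%-area-reduction responder when the analysed visit is at or after the exit

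*Combined protocol and SAP*

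**What the plan says.** Section 7.4.2 gives the endpoint as follows: "The proportion of subjects who achieve 50% reduction of wound size from baseline to interim visit will be calculated for two groups". The analysis is a logistic regression on treatment, baseline wound size and Wagner grade. The population is set at the top of the same section: "The secondary efficacy variables will be analyzed using FAS population". Subjects who stop early therefore stay in the denominator.

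Section 7.7 has one rule for incomplete data. A subject counts as non-healing "if no available data for post-baseline wound/ulcer healing assessment". For everyone else: "Otherwise, the method of last observation carry forward (LOCF) will be used to account for incomplete observation". The reason for stopping plays no part.

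Section 3.4 lists as a discontinuation criterion "Lack of efficacy satisfactory (defined as a worsening of Wagner grade to level of 3"). Section 2.2.1 says that treatment continues up to 16 weeks, until confirmed closure, "or until the subject exited the study as treatment failure". Section 5.4 schedules planimetry every two weeks until confirmed closure "or until the study subject exited the study as lack of efficacy satisfactory".

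Section 5.3.3 says that Wagner grades reflect wound depth and extent of necrosis, and defines the relevant grade thus: "Grade 3: Deep ulcer with abscess, osteomyelitis, or joint sepsis". Surface area is not part of it.

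**The concern.** The rules do not fit together for one kind of subject. An ulcer can shrink at the surface while it deepens or becomes infected underneath. If it reaches grade 3, the protocol treats the subject as a lack-of-efficacy exit. The responder endpoint looks only at area, and neither section 7.4.2 nor section 7.7 has a rule for such exits, so the same subject can be a failure in disposition and a success in a secondary efficacy endpoint.

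At stake are the responder rate in each arm and, if these subjects are unevenly spread, the odds ratio between arms. Uneven spread cannot be ruled out. The investigator knows the assignment (section 4.4), and the blinded evaluator's task is to judge healing from photographs (sections 4.4 and 10.2). No blinded review of Wagner grade or of planimetry is described.

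**Working it through.** The plan states no expected rate for this endpoint and no frequency of grade 3 exits, so there is no figure of its own to reproduce. The first part of the check is a trace through the text; the second is arithmetic on assumed values.

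**Trace for one subject.** Take a baseline area of 10 cm², a last measured area of 4.5 cm², and an exit at grade 3. The reduction is (10 − 4.5)/10 = 55%. What happens depends on where the analysed visit falls:

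- *Analysed visit before the exit.* The area is observed, LOCF plays no part, and a halved area at that visit is a true observation. There is no problem.
- *Analysed visit is the exit visit.* The schedule of assessments labels the premature-discontinuation visit as Visit 10, with ulcer assessment due, and section 3.4 requires end-of-trial procedures. The measured 4.5 cm² is used, and the subject is a responder.
- *Analysed visit after the exit.* Planimetry has ended under section 5.4, section 7.7 carries 4.5 cm² forward, and the subject is a responder.

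Section 7.4.2 calls the time point the interim visit and does not define it, so which case applies cannot be settled.

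**Assumed inputs** (none is in the documents): failure rate *f* of 5–10% per arm; share *s* of failures whose last area is at or below half of baseline, 30–60%.

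**Overstatement of one arm's responder rate** = *f* × *s*:

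- 5% × 30% = 1.5 points; 5% × 60% = 3 points
- 10% × 30% = 3 points; 10% × 60% = 6 points

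With 118 subjects per arm (section 7.1) this is 118 × 0.015 = 1.8 to 118 × 0.06 = 7.1 subjects.

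**Shift in the between-arm difference** = *f*₁*s*₁ − *f*₂*s*₂. With 10% failures in arm 1 and 5% in arm 2:

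- smallest: 10% × 30% − 5% × 60% = 0 points
- largest: 10% × 60% − 5% × 30% = 4.5 points
- equal shares in both arms: 1.5 points (30%) to 3 points (60%)

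With equal failure rates of 10% and shares of 60% and 30%, the shift is 6 − 3 = 3 points, so equal failure rates do not guarantee an undisturbed comparison.

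**On the odds ratio scale**, if both true responder rates were 60% (assumed), a 4.5-point overstatement in one arm gives (0.645/0.355)/(0.60/0.40) = 1.817/1.5 = 1.21 where the truth is 1.

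**Subjects with no post-baseline area.** The FAS keeps all randomised subjects whether or not treated (section 7.2.1). Section 3.1 defines evaluable as having had at least one dose, and section 7.1 allows 236 − 212 = 24 non-evaluable subjects. Some of these may have no post-baseline area. Section 7.7 gives them a healing status but no explicit area or responder status.

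**The case against.** The strongest reply is that the endpoint is meant to describe surface area, not clinical success. Grade 3 worsening already shows up elsewhere: as non-healing in the primary endpoint, in the secondary endpoint on target-ulcer infection, and in the reasons for discontinuation. On that view a disposition failure with a halved area is no contradiction. This is a coherent position, but the plan does not state it, and a responder endpoint listed under efficacy will be read as benefit. Scoring lack-of-efficacy exits as non-responders is a standard convention, and the area-only version can be kept beside it.

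Other parts of the reply stand and limit the point:

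- If the analysed visit precedes the exit, nothing is wrong. A reader might infer that the problem arises whichever visit is meant; it does not.
- LOCF is not the only route. The exit area may be a measured Visit 10 value. Section 2.2.1 also plans 12 weeks of follow-up for all subjects, so later areas may exist, although no rule says how they would be used.
- A reader might infer that the percentage-change ANCOVA is affected in the same way. Section 7.4.2 says that this analysis uses the actual wound size, which can mean observed values only, so whether LOCF feeds it is unclear.
- A reader might infer that subjects with no post-baseline area fall out of the analysis. Section 7.7 does not say so; its non-healing label could reasonably be applied as non-response.
- The phase 2 result does not support the assumed 30–60% share. Its fall from 577 to 163 mm² covers all 30 Wagner-grade-1 subjects, half of whom healed. If healed ulcers count as zero area and baselines were alike, the unhealed averaged 163/0.5 = 326 mm², a reduction of 1 − 326/577 = 43%, and these were not subjects selected for worsening.
- Section 7.2 defers detail to a separate SAP. No such text with a failure rule is in the document reviewed, but one cannot be excluded.

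**Conclusion.** The point holds in a limited form. As written, a subject whom the protocol treats as a lack-of-efficacy failure can be a 50%-reduction responder at the exit visit and at later visits. Only this secondary endpoint is clearly affected. The primary endpoint is not, because a grade 3 ulcer is not healed and carrying its status forward leaves it unhealed.

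The size is unknown. On the assumed ranges, an arm's responder rate is overstated by 1.5–6 points, and the between-arm difference moves by 0–4.5 points when failures run at 10% against 5%. A reader might infer that the error always favours the arm with more failures. The documents do not support that: the bias follows the product of failure rate and halved-area share, neither of which they give, and an arm that shrinks area more could gain even with equal failures. This is worth correcting because the remedy is cheap, but it does not threaten the main conclusion.

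**What to change.** In section 7.4.2, and in the SAP:

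1. Name the scheduled visit at which 50% reduction is assessed.
2. State that, overriding LOCF, a subject who exited for lack of efficacy at or before that visit is a non-responder.
3. State that a FAS subject with no post-baseline area is also a non-responder.
4. Keep the observed/LOCF scoring as a sensitivity analysis, so that the effect of the rule can be seen.

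It would help to say in the same place whether the percentage-change ANCOVA uses observed values only or LOCF.

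The cost is a few sentences and one derivation flag based on the discontinuation reason and date, which section 3.4 already requires in the CRF. No new data are needed. Responder rates will be slightly lower. The rule should be fixed before the unblinded final analysis, since a choice made afterwards would be open to challenge.
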